5.5. Exploratory Endpoint(s) Analysis

• Incidence of rash

5.5.1. Analysis Methods

Rash is an AE of clinical interest to be assessed by NCI-CTCAE Version 5.0 criteria. Incidence of rash will be summarized descriptively using safety analysis set. Incidence rates will be summarized with frequency and percentage by system organ class (SOC) and preferred term (PT), with all subjects treated with study drug as the denominator. In addition, incidence rate will also be summarized by severity and relationship to the study drug.

5.6. Safety Analyses

The safety parameters to be evaluated are the incidence, intensity, and type of adverse events (AE), vital signs, ECG, and clinical laboratory results.

5.6.1. Extent of Exposure

Treatment duration (in terms of cycles and in months) will be defined as the duration from the date of the first dose of study drug to the date of last dose of study drug. Descriptive summary

statistics for duration of apalutamide treatment (N, mean, SD, median, and range (minimum, maximum)) will be summarized using safety analysis set.

Treatment duration will be calculated as the number of days with dosing record divided by 28 (i.e., expected number of days in a cycle) and 30.4375 (i.e., number of days in a month calculated as 365.25/12).

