5. STATISTICAL ANALYSES

5.1. General Considerations

Study Day will be calculated in reference to the date of first dose of study drug (apalutamide). Positive study days will count forward from Study Day 1. Study Day -1 will be the day before Study Day 1, and all subsequent negative study days will be measured backward from Study Day -1. There will be no Study Day 0.

The first dose starts on Day 1 of Cycle 1.

Unless otherwise specified, baseline value is defined as the closest measurement prior to the first dose of study drug. Change from baseline will be defined as (post-baseline value – baseline value).

Treatment Duration will be calculated as the duration of time from the date of the first dose of study drug (apalutamide) to the date of last dose of the study drug, i.e., date of last dose – date of first dose + 1.

Time to Event endpoints will be calculated as the number of days from the start of the study drug to the date of the event of interest, i.e., date of event of interest – date of first dose + 1. Time to event or duration of event endpoints will be based on the actual date of the event, not visit number or visit label. Confidence intervals of survival function at specific time point will be calculated using Kaplan-Meier method. In case no events have occurred by the given time point, a conservative approach will be used by assuming one event at the time point among subjects still at risk.

Continuous/numerical variables will be summarized using mean, standard deviation (SD), median, minimum, and maximum. Categorical variables will be summarized using count and percentage. In general, means and other measures of central tendency will be displayed with one more decimal digit than collected, and standard deviations and other measures of variability will be displayed with two decimal digits more than collected. For frequency counts of categorical variables, categories for which the counts are zero will be displayed for the sake of completeness. For example, if no subject discontinued due to "withdrawal of consent", this reason would still be included in the table but with a count of 0.

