6.7. Appendix 7 Intervention Compliance

Treatment compliance and dose modifications will be summarized using the safety analysis set.

Percent treatment compliance will be defined as the number of tablets taken during the study divided by the expected number of tablets, multiplied by 100. The number of tablets taken will be calculated based on the number of tablets dispensed minus the number of returned tablets. A

subject's expected number of tablets will be calculated according to the planned treatment regimen. For example, for subjects with no dose modification the expected number of tablets equals the number of assigned tablets per day multiplied by treatment duration (defined in Section 5.6.1), however for subjects with dose reduction the expected number of tablets will be smaller. Subjects with at least one dose modification or with dose interruption and the reason for the dose modification will be summarized by treatment group. ADT is background therapy and its dosing and modifications will be summarized by treatment group.

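### SAP 5.6.1 gives two conflicting rules for treatment duration, and the compliance denominator in SAP 6.7 depends on which one is used

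*SAP*

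**What the plan says.** Three places in the SAP bear on treatment duration.

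- **SAP 5.1** gives an explicit formula in days: "date of last dose – date of first dose + 1".
- **SAP 5.6.1, first paragraph**, says that duration, in cycles and in months, is "defined as the duration from the date of the first dose of study drug to the date of last dose". This is the same span.
- **SAP 5.6.1, second paragraph**, gives a different rule: "Treatment duration will be calculated as the number of days with dosing record divided by 28", with 30.4375 as the divisor for months.

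**SAP 6.7** then builds compliance on that section. The measure is: "Percent treatment compliance will be defined as the number of tablets taken during the study divided by the expected number of tablets, multiplied by 100". Tablets taken are the "number of tablets dispensed minus the number of returned tablets". The general basis for the denominator is that the "expected number of tablets will be calculated according to the planned treatment regimen". The worked case, for a participant with no dose modification, is that "the expected number of tablets equals the number of assigned tablets per day multiplied by treatment duration (defined in Section 5.6.1"). After a dose reduction the expected number is said to be smaller, with no formula.

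**The concern.** One term has two calculation rules, and they differ exactly when doses are missed. The span keeps a missed day between first and last dose in the denominator. A count of days with a dosing record removes it, if a missed day leaves no record. A programmer who follows the cross-reference from SAP 6.7 arrives at the section that holds the second rule and could reasonably apply it. Compliance would then be blind to fully missed days, which it exists to show.

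These summaries carry some weight here. Under the estimand (SAP 5.3.2.3), treatment discontinuation with continued follow-up and other protocol deviations are handled by treatment policy, so the primary estimate does not show how much apalutamide was taken. A reader would look to the compliance and exposure tables for that.

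**Working it through.** The documents state no compliance figure, so there is nothing to reproduce. The check is direct arithmetic.

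**Inputs from the documents**
- 4 tablets per day (Protocol 6.1: 240 mg as four 60 mg tablets).
- 12 cycles (Protocol 4.1) of 28 days (Protocol 6.1): 12 x 28 = 336 days, and 336 x 4 = 1,344 tablets.
- Month divisor 365.25/12 = 30.4375 (SAP 5.6.1), which is correct.

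**Assumptions, not in the documents**
- Fully missed days m range from 7 to 84 of 336 (2.1% to 25%).
- All untaken tablets are returned, a fully missed day has no dosing record, and the first and last days are dosed.

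**Formulas**
- Tablets taken = 4 x (336 - m).
- Span rule: compliance = 100 x 4(336 - m) / (4 x 336).
- Dosing-record rule, with duration kept in days: compliance = 100 x 4(336 - m) / [4 x (336 - m)] = 100 for any m.

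| Missed days | Tablets taken | Span rule | Dosing-record rule |
|---|---|---|---|
| 7 | 1,316 | 97.9% | 100% |
| 28 | 1,232 | 91.7% | 100% |
| 34 | 1,208 | 89.9% | 100% |
| 60 | 1,104 | 82.1% | 100% |
| 67 | 1,076 | 80.1% | 100% |
| 84 | 1,008 | 75.0% | 100% |

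**Part-dose days.** Take 34 days fully missed and another 34 days at 2 of 4 tablets. Tablets taken = 268 x 4 + 34 x 2 = 1,140. The span rule gives 1,140/1,344 = 84.8%. The dosing-record rule gives 1,140/(302 x 4) = 1,140/1,208 = 94.4%. Part-dose days lower compliance under both rules; only the fully missed days vanish under the second.

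**Units.** Taken literally, the dosing-record rule yields cycles or months. For a complete course, 4 x 12 = 48 expected tablets and 1,344/48 = 2,800% compliance. In months, 336/30.4375 = 11.04, 4 x 11.04 = 44.2 tablets, and compliance is about 3,044%. SAP 6.7 needs days, but 5.6.1 does not say so.

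**Exposure.** With 60 missed days, the span rule reports 336/28 = 12.0 cycles and the dosing-record rule reports 276/28 = 9.9 cycles. The exposure table also depends on the choice.

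**Directed holds.** Under the span rule a 21-day hold with no other missed dose gives (315 x 4)/1,344 = 93.75%, unless the hold is taken out of expected tablets. The SAP does not say whether it is.

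**The case against.** A reader might infer that the plan as written pushes compliance to 100%. The documents do not support that as a statement of fact. SAP 6.7 cites the duration as defined in 5.6.1, and the defining sentence there is the span, in agreement with 5.1. SAP 6.7 also bases expected tablets on the planned regimen, under which an unplanned missed day is still expected; the multiplication is offered as an example. The dosing-record sentence may have been meant only to supply the divisors for reporting in cycles and months. Since its result cannot be multiplied by tablets per day, the day formula in 5.1 is the natural choice.

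The inflation also depends on what a dosing record is. For the main study the protocol describes eCRF capture of administration (6.1) and a dispensing log with inventory (6.4). A daily pill diary appears only in the sub-study (Appendix 14). If records are start and stop intervals, or include zero-dose entries, the effect shrinks or disappears.

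A reader might also infer that missed doses are hidden in the exposure table. The opposite holds: counting dosed days shortens reported exposure, so missed days would show there. SAP 6.7 also summarises participants with dose interruption separately.

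All of this stands, and it limits the point to an unresolved contradiction. It does not remove it. The second rule is stated as the calculation, it sits in the section that 6.7 points to, and nothing in the SAP says that it does not apply.

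**Conclusion.** The contradiction is real and should be corrected. SAP 5.1 and the first paragraph of 5.6.1 use the span; the second paragraph of 5.6.1 uses days with a dosing record; 6.7 relies on 5.6.1 without choosing. Under the dosing-record reading, compliance is 100% whatever number of whole days is missed, where the span would show 97.9% to 75.0% over the assumed range.

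That size rests on the assumed number of missed days, on a missed day having no dosing record, and on all untaken tablets being returned. Days after early permanent discontinuation fall outside the denominator under both rules, so neither captures them. The reach is limited to descriptive compliance and exposure summaries in the safety set. No compliance threshold enters the modified intent-to-treat definition or the primary test, and the sample size is unaffected.

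**What to change.** In SAP 5.6.1 and 6.7:

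1. Use one treatment duration in days, last dose minus first dose plus 1, as in SAP 5.1. Divide by 28 or 30.4375 only to report exposure in cycles or months, and use the undivided days in the compliance denominator.
2. State how documented holds and dose reductions enter expected tablets, with a formula in place of the present remark that the number will be smaller. Whether documented holds are subtracted is a matter of convention; the SAP needs to name the one chosen.
3. If the number of days with a dosing record is wanted, define a dosing record and report the count under its own name, separate from treatment duration.

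The cost is SAP wording before database lock. No new data are needed, and study conduct does not change.

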5.6.2. Adverse Events

Subjects will be assessed for adverse events at each clinic visit (as specified in protocol Schedule of activities) while on the study. Adverse events (AEs) will be graded according to the NCI Common Terminology Criteria for Adverse Events (NCI-CTCAE) version 5.0 (published on 27 November 2017) and coded to preferred term and system organ class (SOC) using the MedDRA version 20.0 or later.

All AEs reported on or after the date of first dose until 30 days (inclusive) after the last dose of study drug will be considered treatment-emergent and will be summarized.

AE incidence rates will be summarized with frequency and percentage by SOC and preferred term, with all subjects treated as the denominator, unless otherwise specified. In addition, AE incidence rates will also be summarized by severity and relationship to study drug. Treatment-related AEs are those judged by the Investigator to be at least possibly related to the study drug. AEs with missing severity or relationship to study drug will be classified as severe and treatment-related, respectively. Subjects with multiple occurrences of events will only be counted once at the maximum severity to study drug for each preferred team, SOC, and overall. Deaths that occur within 30 days after the last dose of study drug are defined as on-study deaths.

Summary tables of the following AEs will be provided:

- Overall summary of AEs: the number and percentage of subjects who experienced any AE, number of subjects with Grade 3/4 AEs, any serious adverse event (SAE), any treatment- related AE, treatment related Grade 3/4 AE, any treatment-related SAE, AE leading to treatment discontinuation, related AE leading to treatment discontinuation, AE leading to death, related AE leading to death, and all deaths within 30 days of last dose
- All AEs by SOC and preferred term
- Most frequent AEs by SOC and preferred term (reported in ≥ 5% of subjects in either the investigational or control group)
- All AEs by SOC, preferred term, and toxicity grade
- Grades 3 or 4 AEs by SOC and preferred term
- Grades 3 or 4 AEs by decreasing frequency of preferred term
- Treatment-related AEs by SOC and preferred term
- Treatment-related AEs by SOC, preferred term, and toxicity grade
- Treatment-related AEs by decreasing frequency of preferred term

- Treatment-related Grades 3 or 4 AEs by SOC and preferred term
- Most frequent treatment-related Grades 3 and 4 AEs (reported in \geq 5% of subjects in either the investigational or control group)
- Treatment-related Grades 3 or 4 AEs by decreasing frequency of preferred term
- All AEs that led to death by SOC and preferred term
- All AEs that led to study drug discontinuation by SOC and preferred term. Study drug discontinuation will be determined from the End of Treatment CRF (where reason for termination is "Adverse Event") and the specific AE will be determined from the AE eCRF page (where action taken is "Withdrawn from Study")
- All AEs that led to study drug discontinuation by SOC, preferred term, and toxicity grade
- All AEs that lead to study drug dose modification by SOC and preferred term
- All SAEs by SOC and preferred term
- All SAEs by SOC, preferred term, and toxicity grade
- Deaths by time period (Treatment Phase, Follow-up Phase) and cause of death

Subject listings of all Grades 3 or 4 AEs, all SAEs, AEs that led to study drug discontinuation, dose modification, and all deaths will be provided as well. If there are any AEs attributed to RP (e.g. lymphocele, intraoperative bleeding, postoperative bleeding, urinary incontinence), listings of all AEs (or relevant tables if there is a large of proportion of these subjects) will also be provided.

Narratives will be written for the following subjects in the final clinical study report:

- Subjects who die due to treatment-related adverse events ≤ 30 days after the last dose of study drug
- Subjects who discontinue study drug due to adverse events
- Subjects who have a treatment-related serious adverse event
- Subjects who experience a seizure

Subjects who experience other Grade 3 or higher treatment-emergent adverse events of special interest.

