2. INTRODUCTION

Prostate cancer is the second most frequently diagnosed cancer and the sixth leading cause of cancer death in males worldwide.¹² Treatment aimed at eradicating the primary tumor, typically with surgery or radiation, is unsuccessful in 30% of men, who develop recurrent disease that usually manifests first as a rise in prostate-specific antigen (PSA) followed by spread to distant sites.²⁷ Given that prostate cancer cells depend on androgens for proliferation and survival, a standard treatment for patients with recurrent disease is to lower the level of testosterone by surgical castration or with a gonadotropin releasing hormone (GnRH) agonist or antagonist, commonly referred to as androgen deprivation therapy (ADT).

Apalutamide (ERLEADA[®]) is an orally available, non-steroidal small molecule, which acts as a potent and selective antagonist of androgen receptors (ARs). To date, apalutamide has been approved for the treatment of patients with non-metastatic castration-resistant prostate cancer (nmCRPC) and with metastatic castration-sensitive prostate cancer (mCSPC). Apalutamide is currently being studied for the treatment of prostate cancer at all stages.

For the most comprehensive nonclinical and clinical information regarding apalutamide, refer to the latest version of the Investigator's Brochure (IB)¹¹ and US Package Insert (ERLEADA[®] USPI) for apalutamide.

Common terms used throughout the protocol are noted. The term "study intervention" throughout the protocol, refers to apalutamide + ADT. The term "sponsor" refers to the entities listed in the Contact Information page(s), which will be provided as a separate document. The term "participant" throughout the protocol refers to the common term "subject".

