7. DISCONTINUATION OF STUDY INTERVENTION AND PARTICIPANT DISCONTINUATION/WITHDRAWAL

7.1. Discontinuation of Study Intervention

A participant's study intervention must be discontinued if:

- The participant withdraws consent to receive study intervention
- The investigator believes that for safety reasons or tolerability reasons (eg, AE) it is in the best interest of the participant to discontinue study intervention
- Noncompliance with study intervention administration
- Participants experiencing treatment-related seizure of any grade will have apalutamide permanently discontinued

If a participant discontinues study intervention for any reason before the end of the study, then the last scheduled study assessments should be obtained and scheduled assessments off study intervention should be continued. If a participant misses doses for >28 days, consult the sponsor regarding continuation in the study. If a participant discontinues study intervention due to disease progression, the subsequent treatment including radiation will be captured in the eCRF, if known. Additional participants will not be entered to ensure the protocol-specified number of participants complete the study.

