9.4.5. Safety Analyses

All safety analyses will be made on the Safety Population.

Adverse Events

The verbatim terms used in the eCRF by investigators to identify AEs will be coded using the Medical Dictionary for Regulatory Activities (MedDRA). Any AE occurring at or after the initial administration of study intervention through the day of last dose plus 30 days is considered to be treatment emergent. All reported treatment emergent AEs will be included in the analysis. For each AE, the percentage of participants who experience at least 1 occurrence of the given event will be summarized by intervention group.

Summaries, listings, datasets, or participant narratives may be provided, as appropriate, for those participants who die, who discontinue intervention due to an AE, or who experience a severe or a serious AE.

Parameters with predefined NCI-CTCAE toxicity grades will be summarized. Change from baseline to the worst AE grade experienced by the participant during the study will be provided as shift tables.

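### The SAP picks AEs leading to apalutamide discontinuation by withdrawal from the study, so its tables by term and by grade can omit men who stop the drug but stay in follow-up; the treatment-emergent window also needs reconciling with the protocol

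*SAP*

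**What the plan says.** **Discontinuation AEs.** SAP 5.6.2 uses two forms. "Study drug discontinuation will be determined from the End of Treatment CRF", where the reason for termination is an adverse event. Then "the specific AE will be determined from the AE eCRF page", and the action value it requires there is *Withdrawn from Study*. The rule is attached to the table by system organ class and preferred term; a companion table by toxicity grade and a subject listing follow under the same description.

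Protocol 7.1 says that when a man stops study intervention for any reason before the end of the study, "scheduled assessments off study intervention should be continued". Study withdrawal has its own section and its own list of reasons (Protocol 7.2).

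**Treatment-emergent window.** Protocol 9.4.5 counts as treatment emergent "Any AE occurring at or after the initial administration of study intervention through the day of last dose plus 30 days". Protocol section 2 states that study intervention, "throughout the protocol, refers to apalutamide + ADT". In SAP 5.6.2 the window closes 30 days later than a different reference point: AEs up to 30 days "after the last dose of study drug will be considered treatment-emergent and will be summarized". SAP 5.1 names apalutamide alone when it introduces that term: "Study Day will be calculated in reference to the date of first dose of study drug (apalutamide". SAP Appendix 7 describes ADT as background therapy.

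**The concern.** The discontinuation table shows which events made men give up apalutamide. In a single-arm adjuvant study of men who are free of detectable recurrence at entry, this is one of the main tolerability results. A rule that selects events by departure from the study, when the protocol directs that men who stop the drug should stay, looks for the wrong state. The man is counted as having stopped for an AE, but the AE itself does not reach the table that should name it.

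The window raises a related but separate question. If the protocol's window follows both drugs and the SAP's follows only apalutamide, AEs in a man who stops apalutamide and goes on with ADT could be treatment-emergent under one document and not under the other.

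**Working it through.** **1. Discontinuation AEs: the texts side by side**

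| Place | What it establishes |
|---|---|
| SAP 5.6.2, first half of the rule | Drug stopped for an AE, from the End of Treatment form |
| SAP 5.6.2, second half of the rule | The named AE, only if its action is *Withdrawn from Study* |
| Protocol 7.1 | After stopping, scheduled assessments go on |
| SAP 5.2 | Men who discontinued treatment and men who terminated the study early are separate categories |
| SAP 5.3.2.3, Table 1 | Stopping treatment while continuing in the study is its own intercurrent event, distinct from study withdrawal |

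Let *m* be the men whose End of Treatment reason is an AE, and *s* those of them who remain on study. If the action value means what it says, the table names AEs for at most *m* − *s* men. The documents give neither number. As an illustration only, *m* = 10 and *s* = 8 leaves 10 − 8 = 2 men in the table against 10 on the End of Treatment form.

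**2. Treatment-emergent window: day arithmetic**

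Inputs:
- Apalutamide is given for 12 cycles of 28 days (Protocol 1.1), so a completer's last day is 12 × 28 = 336.
- Cycle *c* Day 1 falls on study day (*c* − 1) × 28 + 1.
- The last 3-month depot is at Month 10, which the Schedule of Activities labels C10/D1: 9 × 28 + 1 = Day 253.
- Assumption for comparison: a 1-month depot last given at C12/D1, 11 × 28 + 1 = Day 309.
- Assumption: ADT continues to its scheduled last dose after apalutamide stops.

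Formulas, using administration dates:
- SAP window end = last apalutamide day + 30.
- Protocol window end, with study intervention read as both drugs = the later of the last apalutamide day and the last ADT day, + 30.
- With early stopping, the protocol window ends on Day 253 + 30 = 283 (3-month depot) or Day 309 + 30 = 339 (1-month depot).

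| Apalutamide stops | SAP window ends | Gap, 3-month depot | Gap, 1-month depot |
|---|---|---|---|
| Day 28 | Day 58 | 283 − 58 = 225 days | 339 − 58 = 281 days |
| Day 84 | Day 114 | 283 − 114 = 169 days | 339 − 114 = 225 days |
| Day 168 | Day 198 | 283 − 198 = 85 days | 339 − 198 = 141 days |
| Day 252 | Day 282 | 283 − 282 = 1 day | 339 − 282 = 57 days |
| Day 336 (completer) | Day 366 | 0 | 0 |

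For a completer the later last dose is apalutamide on Day 336 under either depot, so both windows end on Day 366. The Day 84 gap with the preferred depot is 169 / 30.4375, or about 5.6 months. If Month 10 were a calendar month instead (Day 275), that gap would be 275 + 30 − 114 = 191 days.

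**The case against.** **On the discontinuation rule.** The eCRF is not among the documents. *Withdrawn from Study* may be the form's label for drug permanently stopped, in which case no event is lost and only the wording is at fault. That stands as a possibility, and it is why the fix starts with the form.

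Some men who stop for an AE will also leave the study. Protocol 6.1 allows withdrawal after 4 weeks or more off apalutamide, following discussion with the sponsor, and Protocol 7.2 lists seizure and investigator's discretion. A reader might therefore go too far in inferring that the table would be empty; that would require every such man to stay, which the documents do not say.

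A reader might also infer that the safety tables as a whole miss these AEs. They do not. The events remain in the all-AE tables and, where they qualify, in the Grade 3/4, treatment-related and SAE tables. SAP 5.6.2 also requires a narrative for each man who discontinues study drug because of an AE, and the End of Treatment form still counts him. What is at risk is the tables by term and by grade, and probably the listing.

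**On the window.** The protocol uses its own term inconsistently. Despite the definition in section 2, the Synopsis, section 6.1 and Appendix 12 use study intervention for apalutamide alone, and the start of AE collection and the Treated set are tied to apalutamide. The SAP's reading therefore has a basis. No section says that ADT continues after apalutamide stops early. If both stop together, the windows coincide. AEs are collected to the last study procedure (Protocol 8.3.1), and the SAP's listings of Grade 3/4 AEs, SAEs and deaths carry no stated treatment-emergent limit. All of this stands, and it reduces the window issue to a definition to be reconciled.

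**Conclusion.** The discontinuation rule is wrong as written. It uses departure from the study to identify events that ended the drug, although the protocol and the SAP's own disposition and estimand sections separate the two. The affected tables would disagree with the End of Treatment count by the number of men who stop for an AE and remain on study. That number cannot be derived from the documents. The conclusion assumes the action value carries its literal meaning.

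The window is a secondary point. The two definitions differ on their face, and SAP Appendix 2 records no change from the protocol. The difference is zero for completers and arises only if a man continues ADT after stopping apalutamide early: 169 days for a Day 84 stop with the preferred depot, and 1 to 281 days across the early-stop cases worked above. A reader might infer that harm is certainly undercounted in such men. The documents do not support that, because the protocol's usage is mixed, ADT continuation is not stated, and later AEs are still collected. The loss, if any, is from treatment-emergent summaries and not from the database.

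Neither point touches the primary efficacy test.

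**What to change.** 1. Check the action-taken code list on the AE page. In SAP 5.6.2, select discontinuation AEs by the value that means apalutamide permanently discontinued, whatever the man's study status, and apply the same rule to the tables by term and by grade and to the listing. If *Withdrawn from Study* on the form does mean drug withdrawn, correct the SAP wording to say so.
2. Reconcile the treatment-emergent definition between Protocol 9.4.5 and SAP 5.6.2 by stating which last dose closes the window. If the apalutamide-only window is kept, record and explain it in SAP Appendix 2.

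The cost is SAP text and table programming. AEs are already collected through the last study procedure, so no new data are needed.
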